### Enrollment and Informed Consent Considerations:

As described in more detail in section 11, the study will have a waiver of informed consent for research purposes, but subjects will be able to give clinical consent/assent for the V-CST referral and participation. As with usual care, patients do not have to enroll in any program they are not interested in and can stop at any time.

### Randomization:

The UMB team will de-identify and sort screening log and create an enrollment log with each participant assigned a unique study identifier for randomization. Participants will be allocated by a random number sequence in a 1:2 ratio into the intervention or control arms within each site. The study biostatistician will create the random sequence that the HCSs will apply for the random allocation of participants. The sequence will be created using block randomization with size of 4 to ensure balance across time.

At each HCS, clinicians will offer referral for V-CST to participants who were randomly assigned to the intervention group. The referring physician will meet the patient in clinic or contact the patient by phone to offer the referral. The referral will describe what participation entails, including the schedule of V-CST sessions, the use of the online meeting platform, and the expectations of participants' caregivers. To be consistent with real-world clinical practice, blinding will not be used (Dal-Re et al., 2018): the referral

sites will make referrals to the V-CST facilitator team following standard treatment referral protocols, which include the names and contact information of the patients who will be referred.

Patients who are referred for V-CST will be contacted by CaringKind using their standard procedures to enroll referred patients in V-CST.

Attendance in a V-CST orientation session, scheduled at least one to two weeks prior to S1, will be required to verify each participant's capacity to participate in V-CST. The V-CST orientation sessions will be held per CaringKind's SOC protocol. The orientation process is internal to CaringKind, not a part of this study protocol. During the orientation session, the V-CST facilitator will provide an overview description of V-CST, will review caregiver expectations, will verify participants' abilities to use both the audio and visual components of Zoom, and will provide participants an opportunity to meet the V-CST facilitator and to ask questions. Orientation participants who are verified to be able to participate in V-CST will be emailed a Zoom link calendar invite for the 14 sessions. Orientation participants who are determined during the orientation session to be unable to participate (e.g., if they are unable to access Zoom) will be advised by the CaringKind team that they are unable to participate and their HCS clinician will be notified of this outcome. Referrals for V-CST will stop once 56 participants are referred to CaringKind or when all seven V-CST groups have begun.

Enrollment and randomization were completed while UMB was the lead coordinating site. All data in screening process will be transferred after regulatory approval of UMass as the lead coordinating site.

## **5 STUDY INTERVENTIONS**

### **5.1 Interventions, Administration, and Duration**

The intervention introduced in the pilot pragmatic trial is V-CST referral by physician. V-CST referral will be provided to 56 patients who are randomly allocated to the intervention group. CST is an evidence-based group therapy that is recommended for people with a diagnosis of mild to moderate dementia. In this study, CST will be delivered online via Zoom and referred to as virtual CST (V-CST). CST is administered twice weekly over a seven-week period for a total of 14 sessions. At each group session, there will be a total of up to eight participants, and the sessions typically last between 45 minutes to 1 hour and are co-facilitated by two CST-trained facilitators from CaringKind: One facilitator leads the V-CST sessions (lead facilitator), while the other provides participant support (facilitator). To help with adherence rates, reminder emails are sent to participants on the morning of the session, and adherence is captured by CaringKind recording participant attendance at each session per standard of care.

Facilitators ensure privacy and protect safety by providing password protected Zoom sessions. A meeting password is required, and the 'waiting room function' is used to ensure that only those who are intended to join the meeting are admitted.

**Adverse effects:** Some people with dementia may have difficult or traumatic memories, and sensitivity is required not to push group members into sharing painful memories. Additionally, current affair discussions involve topics that members may find uncomfortable to discuss. To mitigate these events, the group members will be able to choose from a list of topic discussions. However, should a participant become upset during the discussion, the facilitators will determine if the person can remain in the group; if the participant is unable to remain in the group (e.g., due to uncontrolled anger), the facilitator will remove that participant from the group to provide him or her private space to discuss what happened. The lead facilitator will inform the HCS of adverse events. Facilitators will respond to adverse events per their SOC protocol at CaringKind. Adverse events will be reported to the HCS clinicians following reporting

guidelines detailed below in section 7. Topics that elicit such events will be removed from the V-CST protocol.

## **5.2 Handling of Study Interventions**

V-CST referral will be handled by the patient's physician following guidelines that align with the physicians' standard referral practices and that use the V-CST facilitators' orientation guide to describe the nature of V-CST, describe risks of participating (such as risk to privacy due to the nature of group therapy), and verify patient assent for the physician to make the referral. When providing V-CST referrals, physicians will meet the patient in clinic or contact the patient by phone to offer the referral. The referral will describe what participation entails, including the schedule of V-CST sessions, the use of the online meeting platform, and the expectations of participants' caregivers. The referral sites will make referrals to the V-CST team following standard treatment referral protocols, which include the names and contact information of the patients who will be referred. V-CST will be administered per SOC protocol at CaringKind. The V-CST procedures described below are part of standard of care at CaringKind and have not been augmented or changed for this protocol.

When delivering V-CST, facilitators will adhere to its 18 principles as specified in the CST facilitator manual and standard of care procedures (Spector et al., 2006):

- 1) Mental stimulation: Improving cognition and communication through mentally stimulating discussions. The first aim of CST is to mentally stimulate and get participants' cognitive functions active and engaged.
- 2) New ideas, thoughts, and associations: Encouraging new ideas and opinions by making new semantic connections. This encourages new ideas, thoughts, and associations, rather than mere memory recall of information previously learned. For example, during the current affairs discussions, rather than introducing familiar topics, participants are encouraged to discuss new topics.
- 3) Using orientation, sensitively and implicitly: Integrating orientation information into general discussion. Formal orientation is to be conducted individually with each participant prior to participating in V-CST. Informal orientation will be conducted in a subtle way in the beginning of each group. Orientation information will be displayed by the V-CST facilitator via the Zoom "share screen" function, and during the discussion the facilitator will offer orientation questions, such as, "Do you think the weather today is hotter/colder than usual for this time of year?"
- 4) Opinions rather than facts: Using topics to generate opinions rather than testing facts to mitigate incorrect answers from participants. The V-CST group should never feel like a memory test. Rather, the strengths of individual participants will be the focus of intervention delivery.
- 5) Using reminiscence as an aid to the "here and now": Comparing old and new information to promote orientation. Using memories helps to tap into a strength that many people with dementia have for recalling experiences from much earlier in their lives. Additionally, such reminiscence is often an enjoyable activity for participants.
- 6) Physical movement: Exercising motor skills through movement and games. Mild exercise components such as lifting arms in sequence are incorporated into V-CST sessions when appropriate. Movement is encouraged at the beginning of every session, but also is limited both to maintain safety and to maintain visual and audio connection with the participants.

- 7) Providing triggers and prompts to aid recall and concentration: Supporting learning through multisensory cues and an information board. A combination of senses are stimulated through the activities in the session. Memory works much better when not relying on only one sense. Oftentimes, visual cues are used during the sessions, such as by using the “share screen” feature, and a variety of sounds are incorporated into the sessions as well.
- 8) Continuity and consistence between sessions: Using consistency throughout sessions helps promote continuity and familiarity. Groups always start and end in the same way. Memory and learning are supported through the provision of continuity and consistency between sessions.
- 9) Implicit (rather than explicit) learning: Let learning and remembering happen naturally. Genial facilitation will encourage participants to experience V-CST groups in a fun way as opposed to viewing these sessions as learning experiences.
- 10) Stimulating language: Promoting communication and conversation. The sessions are designed to stimulate language and promote communication and conversations amongst participants.
- 11) Stimulating executive functioning: Using activities to support planning and organizing. Executive functioning involves sequencing, planning, and organizing. Several of the V-CST sessions exercise executive functioning skills.
- 12) Person-centered: Seeing the person and their uniqueness. Each person in the group is unique, with a lifetime of experiences that have shaped their personality and attitudes, leading to a variety of skills, interests, preferences, and abilities. Participants’ strengths will be focused on, rather than concentrating on areas of weaknesses.
- 13) Respect: Respect and dignity for all. It is imperative to show respect by learning what is important to each participant, and to value the diversity of views, opinions, and beliefs in the group.
- 14) Involvement and inclusion: Keep everyone involved. The group facilitator should not be doing most of the talking. Group members should be encouraged to address their contributions to one another. The group can also be involved in helping to plan future sessions, such as deciding upon what topics to discuss at the next session.
- 15) Choice: Activities are flexible and should be adapted to each participant’s strengths. The group program is not prescriptive. Group members should always be offered choices, and alternative activities and approaches should be available to fit the needs of the group. Offering choices allows group members to become more involved, especially in activities that allow them to identify with their group when selecting a group name and group song. A choice of activities is offered for each session. The facilitator can choose from two activities designed for each session, mix ideas across sessions, or incorporate their own ideas into the session if appropriate.
- 16) Fun: Make it fun and enjoyable. Groups should provide a learning atmosphere that is fun and enjoyable. Members’ brains should be stimulated, as should their sense of humor.
- 17) Maximizing potential: Optimize the learning environment to support the peoples’ potential. People with dementia can learn, given the right environment. Give people time, do not overwhelm participants with information and provide them just enough prompting to enable them to carry out the activities independently. This will increase exposure to success, which will also aid in learning and enjoyment.

- 18) Building/strengthening relationships: Becoming friends. The group sessions will help members to get to know each other better and can strengthen relationships between the members and facilitators.

Each of the V-CST sessions is comprised of an introduction, a main activity, and a conclusion. There is a manual to provide guidance and examples for trained facilitators (Spector et al., 2016), and it emphasizes the flexibility of CST delivery to align with group interests, needs, and preferences. An outline description of the three main parts of a V-CST session is provided below.

**I. Introduction (Duration: 10 minutes)**

- i. Group name and theme song: During the first session, identify a group name and group theme song. After today's session, please begin all future sessions by greeting each group by their group name and sing your group song.
- ii. Orientation: Discuss day, month, year, season, weather, time, name and location
- iii. Icebreaker: Question for all to enhance group cohesion
- iv. Discussion: Current events (using newspapers or photographs)

**II. Main Activity (Duration: 25 minutes):**

Most sessions include a choice of two activities selected to align with the level of function and interests of the group. All activities can be adapted to align with group interests and capacity. Activity suggestions from the manual for group facilitators are shown in Appendix A. The activity themes for each of the 14 sessions are listed below.

1. Physical Games
2. Sounds
3. Childhood
4. Food
5. Current Affairs
6. Faces/scenes
7. Word Association
8. Being Creative
9. Categorizing Objects
10. Orientation
11. Using Money
12. Number Games
13. Word Games
14. Team Quiz

**III. Conclusion (Duration: 10 minutes)**

- i. Thank everyone for participating
- ii. Members sing the theme song again
- iv. Introduce next week's content
- v. Seek feedback about the session

**5.3 Concomitant Interventions**

**5.3.1 Allowed Interventions**

All drugs and/or treatments/interventions are allowed, including rescue medications, while in the study.

**5.3.2 Required Interventions**

No concomitant interventions are required.

### **5.3.3 Prohibited Interventions**

No classes of medications, devices, etc. are prohibited while the participant is in the study.

### **5.4 Adherence Assessment**

Adherence will be assessed by documenting several process measures using data captured in standard practice by CaringKind, including:

1. referral acceptance rate (percentage of participants offered V-CST referral who accept referral)
2. enrollment rate (percentage of participants offered V-CST referral who enroll in V-CST)
3. attendance at each of the 14 V-CST sessions. Attendance will be tracked over the course of the pilot.

## **6 STUDY PROCEDURES**

Study procedures, including the schedule of evaluations and description of evaluations, are described below.

## 6.1 Schedule of Evaluations

Assessment	Pre-Treatment Data Screening (Day -90 to -30)	Treatment Enrollment (Day -30 to -1)	Treatment Group 1-7 (Day 0 to 200)	Post-Treatment Data Screening (Day 61 to 275)
Inclusion/Exclusion criteria	X			
Randomization	X			
Demographics	X			
Diagnoses	X			
Medications	X			
Cognitive function	X			X
Referral acceptance rate	X			
Enrollment rate		X		
Attendance			X	
Attrition			X	
Therapy administration form			X	
Weekly Monitoring Participant Progress reports			X	
Adverse Events			X	

NOTE: Day 0 = Date of V-CST Group 1, Session 1

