## **1 STUDY OBJECTIVES**

### **1.1 Primary Objective**

Cognitive Stimulation Therapy (CST) is an evidence-based non-pharmacological group therapy shown to benefit people with mild cognitive impairment and/or mild to moderate dementia. A Cochrane Review of 15 RCTs of CST integrated data in meta-analyses for 718 participants (407 receiving cognitive stimulation, 311 in control groups) and showed "a clear, consistent benefit on cognitive function was associated with cognitive stimulation (standardized mean difference (SMD) 0.41, 95% CI 0.25 to 0.57). This remained evident at follow-up one to three months after the end of treatment" (Woods et al., 2012). Consistent with these meta-analysis findings, the present study will examine the impact of V-CST on

cognitive function in approximately the same time frame (i.e., within two months) after the end of treatment.

Despite increasing availability of CST worldwide, including in Connecticut and New York City, access remains limited in the United States. This pilot pragmatic trial will embed V-CST referral into the standard care protocol of diverse health care settings that serve people living with dementia in the state of Connecticut, assess the acceptability of V-CST to people living with dementia, and determine the feasibility of using cognitive test results collected as part of clinical care to evaluate study hypotheses. Collection of these data longitudinally will be leveraged to compare rates of clinically meaningful cognitive change between intervention and control groups.

The two-armed trial will use existing data collected in standard care to test the primary hypothesis,

*H1: Clinically meaningful cognitive decline will be less common in the intervention group than the control group.*

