#### **4.1 Inclusion Criteria**

Participants must meet all the inclusion criteria to participate in this study, to be assessed in clinic or by record review at each site:

- Diagnosis of Mild Cognitive Impairment or Mild to Moderate Dementia
- MoCA score of 10 to 26 OR SLUMS score of 10 to 26 OR MMSE score between 13 and 24 recorded as present  $\leq$  24 months before the record review
- English-speaking
- Visit expected to be scheduled to include cognitive screening 6 to 12 months after record review.

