### **6.2.4 Post-V-CST Data Screening**

Post-V-CST data screening will be conducted by the referring physician after the 14 V-CST sessions have been held.

At this time, post-intervention data on medications and cognitive screening scores will be abstracted from HCS records on the study participants. Post-treatment data screening will conclude with HCSs uploading the abstracted data to the project Sharepoint file.

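### The follow-up timings conflict: outcome data close at Day 275 although eligible visits run to about Day 335, and no index date is given for controls

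*Combined protocol and SAP*

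**What the plan says.** The timing of the primary outcome is described in five places.

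- Section 4.1 makes eligibility depend on a future visit: "Visit expected to be scheduled to include cognitive screening 6 to 12 months after record review". The qualifying baseline score may date from up to "24 months before the record review".
- Section 6.1 gives three spans: "Pre-Treatment Data Screening (Day -90 to -30", "Treatment Group 1-7 (Day 0 to 200" and "Post-Treatment Data Screening (Day 61 to 275". All are on one clock: "NOTE: Day 0 = Date of V-CST Group 1, Session 1".
- Section 6.2.4 sets the trigger for collecting follow-up data: "Post-V-CST data screening will be conducted by the referring physician after the 14 V-CST sessions have been held". The data are then abstracted for the study participants generally.
- Section 1.1 says that cognition will be examined "in approximately the same time frame (i.e., within two months) after the end of treatment".
- The Précis (Interventions and Duration) gives the study one year from screening to completed analysis. It gives each participant up to one year from the start of referral to the follow-up visit.

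Section 9.5 analyses all randomized patients as assigned and plans multiple imputation for outcomes that cannot be retrieved. Neither Section 9.4.1 nor Section 9.5 says which test counts as the follow-up score when the record holds more than one.

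**The concern.** The primary outcome is a change of at least 2 points between two routine-care tests, so the timing of those tests is part of its definition. The timing passages cannot all hold, and no rule settles which one governs.

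Three things are at stake. First, tests that meet the eligibility expectation would be excluded only because the data window closes too early. Second, the trial is open-label. Without an index date for controls, or for intervention patients who decline or never start V-CST, staff who know the allocation would have to decide which test to use, and the two sites could decide differently. Third, a main purpose of this pilot is to show that routine data can evaluate V-CST, so a workable outcome window is itself one of its products.

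**Working it through.** **Inputs.** Review on Day -90 to -30, groups on Day 0 to 200 and outcome window Day 61 to 275 (Section 6.1). Visit 6 to 12 months after review, taken as 182 to 365 days, and baseline up to 24 months before review (Section 4.1). Course length 7 weeks = 49 days (Section 5.1). 56 and 112 participants (Section 9.2). 50% decline rate and a 22-point difference (Section 9.5).

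**1. Eligible visits against the data window.** Earliest: -90 + 182 = Day 92. Latest: -30 + 365 = Day 335. The window closes on Day 275, which is 275 + 90 = 365 days after a Day -90 review but only 275 + 30 = 305 days (10.0 months) after a Day -30 review.

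For review day r and a visit uniform over the 183 days from r + 182 to r + 365, the share after Day 275 is (r + 365 - 275)/183 = (r + 90)/183.

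| Review day | Share of qualifying visits after Day 275 |
|---|---|
| -90 | 0/183 = 0% |
| -60 | 30/183 = 16.4% |
| -30 | 60/183 = 32.8% |
| uniform on -90 to -30 | 30/183 = 16.4% |

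Applied to all participants, 0.164 x 168 is about 28 (about 9 of 56 and 18 of 112). The share does not depend on arm.

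The lower limit excludes nothing, since Day 61 is 31 days before the earliest qualifying visit. It does admit tests earlier than eligibility foresees: Day 61 is 91 days, about 3 months, after a Day -30 review.

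**2. The two-month statement.** Group 1 ends about Day 49. The window then runs from 61 - 49 = 12 to 275 - 49 = 226 days (7.4 months) after its end. For a Group 1 patient reviewed on Day -30, the earliest qualifying visit is Day 152, already 103 days after treatment. For a group ending on Day 200 the window closes 75 days later, which is close to two months.

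**3. Index date.** Completion of 14 sessions defines a date for V-CST attenders. A control has no such date, nor does an intervention patient who never enrols, yet Section 9.5 keeps both in the analysis.

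**4. Span of change.** 24 months before review plus 12 months after it gives up to 36 months around a 7-week course. The H1 covariates (comorbidities, baseline cognition, psychotropic count, diagnoses, site) include no time term.

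**5. Duration.** Day -90 to Day 275 is 365 days, which uses the whole one-year study before any analysis.

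**6. Effect on power.** The plan's 80% reproduces: 50% against 28% with 112 and 56 participants, two-sided 5%, gives 78.9%. No allowance for loss is included. Complete-case power with equal loss in both arms is 74.4% at 10% loss and 69.1% at 20%. At 16.4% loss (about 46.8 and 93.6 participants) it is about 71%.

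**The case against.** The best defence is that Day 61 to 275 is a study-level span over staggered groups, from 12 days after Group 1 ends to 75 days after Day 200, and that Section 1.1 says only approximately two months. This stands as far as it goes: on that reading the window does not conflict with the group schedule. It does not move the Day 275 close, and it gives no group-specific windows that would bring early groups near two months.

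A reader might infer that follow-up is tied to V-CST completion in the intervention arm only, so that follow-up length and loss differ by arm. The documents do not support this. Section 6.2.4 covers the study participants generally, and its trigger can be read as one calendar date for all. Section 9.5 is intention-to-treat, and no rule discards intervention tests taken before session 14. Even if such a rule were assumed, with evenly staggered groups, the mean test day would differ by only about 9 days (Day 207 against 198).

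A reader might also infer that many intervention tests precede the end of the participant's own group. That needs review at Day -90 to -30 even for the last group. The Précis speaks of open enrollment until groups fill or have begun. If review comes 30 to 90 days before a participant's own group starts, the earliest qualifying visit is 92 days after that start, beyond the 49-day course. This reading makes the Day 275 cut-off worse: for a group starting on Day 151, qualifying visits fall on Day 243 (151 - 90 + 182) to Day 486 (151 - 30 + 365). It does so in both arms.

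Multiple imputation is planned, and Section 1.2 lists data completeness and follow-up attendance as process measures. Both help, but imputation cannot decide which test is the outcome, and it is a poor substitute for scores that are already in the record. Old baselines are balanced in expectation by randomization, and H1 adjusts for baseline cognition, so they cost precision only.

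**Conclusion.** The concern holds as an inconsistency among the timing passages. Followed as written, the plan excludes qualifying visits on Day 276 to 335 in both arms: between 0% and 33% depending on review date, and about 16% on average. The average rests on uniform review and visit dates; the documents give neither the actual dates nor a loss rate. The corresponding complete-case power is about 71% against 78.9% as reproduced, before imputation.

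The two-month statement fails for early groups and is nearly right for the last. The missing index date for controls and non-enrollers is a gap in the definition. In an open-label trial it creates a risk of follow-up that differs by arm, but the documents do not show that this occurs. Baselines up to 24 months old add noise, not bias.

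**What to change.** - Reconcile the timing statements in the Précis (Interventions and Duration) and Sections 1.1, 4.1, 6.1 and 6.2.4.
- Define one outcome window and one visit-selection rule, counted from record review or randomization, identical in both arms and independent of V-CST group dates. Fix the rule before outcomes are seen by arm.
- Run the final record pull at Day 335 or later.
- Remove or correct the two-month statement in Section 1.1.
- Report time from review to test by arm and, for the intervention arm, the share of tests done before the participant's group ended. A window independent of group dates may include some such tests, so the share should be visible.
- Optionally, add time from baseline test to randomization as a pre-specified covariate in H1 and H2.

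Section 4.3 says that enrollment and randomization are complete, so the change concerns the outcome definition and the data pull, not who is eligible.

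**Cost.** Protocol and SAP wording, and a pull about two months later (335 - 275 = 60 days). No visits or tests are added. The one-year study duration must be restated, since Day -90 to Day 335 is 425 days before analysis begins.
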